STU#:00203896

PROTOCOL TITLE: Impact of Companion Presence during Placement of Neuraxial Analgesia

PRINCIPAL INVESTIGATOR:

[name].
Department of Anesthesiology
[contact]
[contact]

VERSION NUMBER:

Version 1.0

VERSION DATE:

11/11/2016

OBJECTIVES:

The purpose of the study is to evaluate the impact of the presence of a companion during epidural catheter placement for labor analgesia. It will be focused on parturients having their first child. Additionally, it will investigate the effect of ethnicity, health literacy (as evaluated by the Newest Vital Sign questionnaire), catastrophizing (as evaluated by the Pain Catastrophizing Scale), and the relationship of the companion to the parturient. We hypothesize that there may be specific subgroups in which the parturients satisfaction is improved by the presence of a companion during labor epidural catheter placement; however, a significant improvement in maternal anxiety, when including all participants, will not be appreciated.

BACKGROUND:

Currently at our institution, the support team for the parturient in labor is asked to exit the room during the placement of the labor epidural catheter. However, there has been a recent movement in many institutions to allow a companion to be present during this perceived stressful procedure, as it may improve maternal satisfaction and anxiety, in a similar fashion as having a support person present during a cesarean delivery under neuraxial anesthesia.

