During the month of August, a small, random sampling of parturients in the labor and delivery ward at Prentice Women's Hospital were surveyed as to whether they would want a companion present during the placement of a labor epidural catheter for analgesia. Those that already had a labor epidural catheter in place were asked if they would have liked to have a companion present during the placement, while those who did not yet have one placed were asked if they would choose to have someone present if they were given the choice. An overwhelming number of parturients (29/34) stated that they would choose to have a companion present for the procedure. Additionally, of those who would not have chosen to have someone present (5/34), two stated that they still would have appreciated being given the choice. Our study would add to the two prior studies by specifically demonstrating whether giving the parturient her choice in the presence of a companion improves satisfaction, as well as anxiety, during the placement of a labor epidural catheter for analgesia.

INCLUSION AND EXCLUSION CRITERIA:

Parturients will be screened for eligibility on a basis of reason for admission to the labor and delivery ward. Those that are being induced for labor or arrive in spontaneous labor will be considered. Those admitted for a planned procedure, other than labor, will not be eligible.

Companions will be approached on the labor and delivery unit 8th and 9th floor Prentice Women's Hospital and the study team member will introduce the study as well as the requirements for participation. A verbal consent will be obtained.

Physician Participants

A) Attending Physicians will be approached on the labor and delivery unit on the 8th floor Prentice Women's Hospital to participate in the study before the epidural catheter has been placed. Risks and benefits as well as responsibilities of completing the questionnaire will be discussed.

B) Resident Physicians and Anesthesiology Fellows

The resident physician or fellow will be approached on the labor and delivery unit on the 8th floor Prentice Women's Hospital in the Anesthesiology work room before the epidural catheter has been placed. Risks and benefits as well as responsibilities of completing the questionnaire will be discussed as well as the ability for the resident to opt out of study participation.

Inclusion:

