Parturients will be included if they are delivering the first child and are planning to labor with neuraxial analgesia. Additionally, there will need to be sufficient time before delivery to allow the completion of the Pre procedure questionnaire, State-Trait Anxiety

Inventory (STAI) questionnaire both before and after the procedure, as well as the Newest Vital Sign questionnaire and the Pain Catastrophizing Scale questionnaire before the procedure. They will be included if they are ASA 2. Furthermore, they be required to read and comprehend the English language, as the Newest Vital Sign questionnaire requires them to read and interpret a nutrition label.

Physician Inclusion:

Anesthesiology Attending, Fellow or Resident Physicians who participants in the placement of the epidural catheter placement

Companion Inclusion:

Primary companion identified by parturient over the age of 18

Exclusion: Parturients will be excluded if they are receiving neuraxial anesthesia for a cesarean delivery, external cephalic version, or other non-labor procedure. They will also be excluded if they begin to push for delivery before completion of the STAI questionnaire following labor epidural catheter placement. They will be excluded if there is no support person present at the time of the neuraxial procedure. They will be excluded if they are ASA 3 or greater, or if they have a contraindication to receiving any of the medications routinely used in the placement of a labor epidural catheter (lidocaine, bupivacaine, epinephrine, fentanyl). Adults who are unable to consent and minors will be excluded.

STUDY-WIDE NUMBER OF PARTICIPANTS:

The total number of participants has been determined to be 75 per group, for a total of 150.

STUDY-WIDE RECRUITMENT METHODS:

Potential participants will be recruited while they are on the labor and delivery ward at Prentice Women's hospital, prior to the placement of a labor epidural catheter. They will be approached by a member of the research team.

Potential participants will be identified by interview and personal history, as well as by anesthesia and obstetric notes in the electronic medical record.

No advertisements will be used to recruit participants for the study.

MULTI-SITE RESEARCH:

N/A

STUDY TIMELINES:

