Participants will be asked to fill out the STAI questionnaire to assess the level of anxiety prior to placement of the labor epidural catheter, and before knowing their group assignment. They will then complete the pre procedure questionnaire. This questionnaire asks about expectations she has for the labor epidural procedure. They will then be given the page of the Newest Vital Signs questionnaire with the Nutrition Facts, and be asked the 6 questions by the recruiter. Then they will be asked the Pain Catastrophizing Scale questionnaire with 13 statements, and asked to respond as directed by the instructions stated by the researcher. They will then be asked who their primary support person is. A form will be handed to that person to confidentially record if he/she would prefer to be present for the procedure. This form will be collected from the support person, and without the parturient aware of the support person's response, she will be asked for her preference with regard to the presence of a support person in

the room, which will be recorded on this form as well. Finally, she will be asked which ethnicity she most relates to, also to be recorded on this form.

After all these data have been collected, the parturient will be randomized as to whether her companion will be allowed in the room or will be asked to leave. This will not be communicated to the parturient until the time of the labor epidural catheter placement. When she requests the neuraxial labor analgesia, the provider placing the labor epidural catheter will be made aware of which group she has been randomized to, and will either ask the companion to leave for placement, or provide the companion a non-mobile chair to sit on in front of the parturient for placement of the labor epidural. The companion will be asked to remain in the chair. He/she will be asked to focus on the parturient. It will be emphasized that he/she must remain seated and will not be allowed to observe the procedure being performed. This is to prevent loss of consciousness in the companion, which has been documented in the literature (Devore and Asrani, 1978; Crosby and Halpern, 1989). One violation will result in a warning, and after a second the companion will be escorted out of the room and the participant will be removed from the study.

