Participants will be recruited on the Labor and Delivery Ward 8th floor of Prentice Women's Hospital. They will be approached regarding participation if they meet inclusion criteria during chart review or initial pre-anesthesia interview. Both patients in spontaneous labor and those scheduled for induction of labor will be approached if they meet criteria. The GE Centricity computerized board that lists all active laboring parturients is available in the anesthesia work room for review of the current Labor and Delivery census. If the patient is nulliparous she will be approached by a member of the

research team with regard to enrollment in the study. No reimbursement will be offered for participation.

NUMBER OF LOCAL PARTICIPANTS:

A total of 150 participants will complete the study. Half of the participants (n=75) will be randomized to the “companion in the room” group and half (n=75) will be randomized to the “companion out of the room” group. We are anticipating minimal patients who enroll to become ineligible during the study, since the total duration of enrollment is likely less than a couple hours, however we will attempt to recruit 180 participants in total to allow for a 20% drop-out rate, either by choice or by protocol violation.

Resident Participation: A total of 64 participants

Attending Physician: A total of 30 participants

Companion: A total of 150 participants

CONFIDENTIALITY:

Data will be stored in a department server which is password protected. Each study subject will be assigned a study code number. The code will be used to link study data to patient identification (name) in a separate database. Subject data will be stored on secured password protected computers at Northwestern University and Department of Anesthesiology servers. Paper data will be completed by research study team members and will be entered into REDCap. The paper folders will be stored in Arkes Pavilion 10th floor Department of Anesthesiology administrative office via key card controlled front door and key controlled closet. Data access will be password protected and only available to study investigators via REDCap. REDCap access will be controlled by the Principal Investigator. Data both electronic and paper will be destroyed 5 years after manuscript preparation.

PROVISIONS TO PROTECT THE PRIVACY INTERESTS OF PARTICIPANTS:

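### Women who leave by choice after learning their group are covered by over-recruitment rather than followed up, which leaves a pooled comparison of completers open to selection bias

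*Combined protocol and SAP*

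**What the plan says.** NUMBER OF LOCAL PARTICIPANTS states "A total of 150 participants will complete the study", 75 per group, and sets a recruitment target of 180 "to allow for a 20% drop-out rate, either by choice or by protocol violation". Leaving by choice is therefore drop-out, made good by recruiting more women.

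PROCEDURES INVOLVED records the woman's preference about a companion before randomisation. Of the group assignment it says: "This will not be communicated to the parturient until the time of the labor epidural catheter placement". The satisfaction VAS, the pain VAS and the second STAI all follow the procedure.

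BACKGROUND describes usual care at the hospital: "the support team for the parturient in labor is asked to exit the room during the placement of the labor epidural catheter". It also reports a ward survey: "An overwhelming number of parturients (29/34) stated that they would choose to have a companion present for the procedure". The other 5 of 34 would not.

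WITHDRAWAL OF PARTICIPANTS keeps the data gathered before withdrawal, but only to look for characteristics that predict not following instructions. The protocol names no analysis by assigned group, no outcome collection from women who decline their arrangement, no missing-data method, and no reporting of drop-out by arm or preference.

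STUDY ENDPOINTS words the primary question as the effect of a support person on satisfaction where the woman wants one. The power statement under DATA AND SPECIMEN MANAGEMENT compares 75 with 75 and mentions no restriction by preference.

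**The concern.** A woman hears her group before any outcome exists. If she leaves at that point, her primary outcome is lost and another recruit makes up the number. Extra recruits restore the sample size but not the balance that randomisation gave.

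The incentive to leave may not be the same in both arms. If leaving means a return to usual care, a companion-in woman who would rather be alone gets her preferred arrangement by leaving. A companion-out woman who wants her companion does not. In a pooled comparison of completers, the companion-in arm could lose some of the women likely to be least satisfied there, and its mean satisfaction would rise for a reason unrelated to any benefit of a companion. The same loss would affect the pain VAS and the repeat STAI.

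**Working it through.** **The plan's own figure.** 150 x 1.20 = 180, which reproduces the recruitment target. That is 90 randomised per arm.

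**Inputs**
- p, the share of enrolled women who do not want a companion: 5/34 = 0.147, exact 95% CI 0.050 to 0.311. The survey is in BACKGROUND. Applying it to enrolled women is an assumption.
- q, the share of those women in the companion-in arm who leave at disclosure: assumed, 10% to 100%.
- D, the gap in mean satisfaction in the companion-in arm between women who do and do not want a companion: assumed, 20 mm, with 10 and 30 mm as alternatives.

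**How many women.** 90 x 5/34 = 13.2 in the companion-in arm (4 to 28 across the CI). As 13.2/180 = 7%, even the loss of all of them would fit inside the 20% allowance.

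**Shift in the companion-in mean.** After a share q leaves, the unwilling fraction among those who remain is p(1 - q)/(1 - pq). The mean rises by

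shift = D x [p - p(1 - q)/(1 - pq)].

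With p = 0.1471 and D = 20 mm:
- q = 0.10: 20 x (0.1471 - 0.1343) = 0.25 mm
- q = 0.25: 20 x (0.1471 - 0.1145) = 0.65 mm
- q = 0.50: 20 x (0.1471 - 0.0794) = 1.35 mm
- q = 1.00: 20 x 0.1471 = 2.94 mm

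The shift is proportional to D. Half leaving gives 0.68 mm at D = 10 and 2.03 mm at D = 30. All leaving gives 1.47 and 4.41 mm. Across the CI for p, at D = 20, half leaving gives 0.48 to 2.53 mm and all leaving gives 0.99 to 6.21 mm.

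**Against the planned difference.** If 4.7 is in millimetres of satisfaction VAS, the four shifts at D = 20 are 5%, 14%, 29% and 63% of it. The power statement names neither outcome, scale nor SD, so this comparison is conditional.

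**The opposite loss.** Suppose companion-out women who want a companion (29/34 = 0.8529) score 20 mm below the others in that arm and 10% of them do not give outcomes. The companion-out mean rises by 20 x [0.8529 - 0.8529 x 0.9/(1 - 0.0853)] = 20 x (0.8529 - 0.8392) = 0.27 mm. That is about the size of the 0.25 mm above, in the other direction.

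**Restricted comparison.** Among women who want a companion, p = 0 and the shift is zero whatever q and D are.

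**The case against.** The strongest reply is that the primary question concerns women who want a companion, and that preference is recorded before randomisation. Analysed as worded, the unwilling women fall outside it and this mechanism does nothing. That stands, but the plan never commits to the restriction. Its only sample-size statement uses all 75 per group, and OBJECTIVES frames the anxiety hypothesis over all participants.

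A reader might infer that choice drop-out is one-sided and must inflate the result for companion presence. The documents do not support this. Disappointed companion-out women may decline the later forms. Companion-out women are also withdrawn if the companion enters early. Both losses could push the other way. A return to usual care on leaving is a fair inference from BACKGROUND, not a stated rule.

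The inputs are also soft. The 5/34 comes from a ward survey that included women whose catheter was already in place. Women set on being alone have little reason to enrol, since CONSENT PROCESS stresses that preference does not affect grouping, so the share among enrolled women may be lower. The protocol expects few women to become ineligible and gives no separate forecast for quitting.

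Finally, analysis as assigned does not recover the low scores of unwilling women. If a woman who declines is then as satisfied as the willing women, the companion-in mean still rises by pqD = 0.1471 x 0.5 x 20 = 1.47 mm, against 1.35 mm under drop-out. That is correct. The case for as-assigned analysis is that it keeps the randomised comparison intact and guards against selective loss in either direction.

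**Conclusion.** The concern holds as a risk. Followed as written, the plan leaves the comparison to completers selected after they know their group, in a trial where the woman cannot be blinded and the primary outcome is her own rating. A pooled comparison is therefore open to selection bias. The likely direction favours companion presence, on the inference that leaving restores usual care and so changes the arrangement only for companion-in women. The net direction is not established.

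At p = 5/34 and a 20 mm gap, the shift runs from about 0.25 mm if 10% of unwilling women leave, through 0.65 mm (25%) and 1.4 mm (50%), to 2.9 mm if all leave. The leaving share and the gap are assumptions, and so is p for enrolled women. A reader might infer that the bias is a large part of the planned effect. That needs at least half of the unwilling women to leave at this gap, and needs 4.7 to be on the satisfaction VAS, which the protocol does not say. A comparison limited to women who want a companion is not affected by this mechanism.

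**What to change.** In WITHDRAWAL OF PARTICIPANTS, NUMBER OF LOCAL PARTICIPANTS and the statistical paragraph under DATA AND SPECIMEN MANAGEMENT:

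1. Count only withdrawal of consent to data collection as drop-out.
2. For a woman who declines or does not receive her assigned arrangement, still ask for the satisfaction VAS, pain VAS and STAI, and analyse her in the group assigned.
3. Report declined assignments and missing outcomes by arm and recorded preference.
4. State that the primary comparison, in line with STUDY ENDPOINTS, is among women who recorded a wish for a companion, and report the all-randomised comparison as well.

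These changes concern data collection and analysis only. They do not set who stays in the room.

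Items 1 to 3 cost some wording and one tick-box, because preference is already collected. The as-assigned estimate is the effect of assignment, not of actual presence, and crossovers may shift it in either direction. Item 4 has a cost in power. If 29/34 applied to enrolled women, 75 x 29/34 = 64 per group would remain. Scaling the stated 81% power by normal approximation gives (1.960 + 0.878) x sqrt(64/75) - 1.960 = 0.66, or about 75%, so the sample size should be rechecked.
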